#### 10.6.2.2 SARS-CoV-2 Neutralizing Antibodies

In subjects who tested seronegative to the N protein for SARS-CoV-2 at baseline (see Section 10.6.3), seroconversion is defined as a fold increase above 1 in SARS-CoV-2 neutralizing antibody titer.

In subjects who tested seropositive to the N protein for SARS-CoV-2 at baseline (see Section 10.6.3), the definition for seroconversion is a fold increase above 2 in SARS-CoV-2 neutralizing antibody titer versus baseline.

### 10.6.3 Retrospective SARS-CoV-2 Serology Baseline Status and during the Trial

The retrospective SARS-CoV-2 status at baseline and throughout the trial is based on Anti-SARS-CoV-2 NCP ELISA (IgG) EI 2606-9601-2 G by Euroimmun.

Serology status for baseline:

- A ratio below 0.8 is defined as seronegative
- A ratio equal and above 0.8 and below 1.1 is a borderline case and will therefore also be defined as seronegative.
- A ratio equal and above 1.1 is defined as seropositive

If either the swab PCR performed at baseline is seropositive or the local ELISA serology assessment is seropositive, the subject is seropositive at baseline independently of the above cut-off values.

Serology status during the trial:

A subject categorized as seropositive at baseline will remain seropositive independently of later assessments, per the algorithm detailed for baseline assessment. A subject categorized as seronegative at baseline but assessed as seropositive at any post-baseline sample will be categorized as seropositive at this sample visit and beyond.

If either the PCR swab performed post-baseline or the local ELISA serology assessment collected post-baseline is seropositive, the subject is seropositive at that visit and beyond independently of the above cut-off values.

The baseline sample is defined as the sample taken at the screening/clinic visit 1 – day 1.

For subjects in which the retrospectively baseline/post-baseline serology status cannot be determined these will not be included in the counts of seroconverted subjects.

This definition is used throughout the endpoints for the sub-analysis.

### 10.6.4 Evaluation of Infection

Virologically-confirmed SARS-CoV-2 infections are measured by RT-PCR at clinically determined time points throughout the trial.

Subjects with asymptomatic SARS-CoV-2 infections will be measured by retrospective serology at predefined time points (see section 10.6.3 for additional details) and RT-PCR results. The selection of asymptomatic subjects will be based on the exclusion of subjects with adverse events of special interest indicating COVID-19 disease.

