9.3 Laboratory Testing for COVID-19 Disease

As a baseline assessment, a RT-PCR test for SARS-CoV-2 will be performed in all subjects. Testing will be done for SARS-CoV-2 spike protein to evaluate vaccine-induced immune responses as well as for SARS-CoV-2 N-antigen (not contained in the vaccine construct) to evaluate immune responses induced by natural infection. This will allow to retrospectively define the subject's serology status, including the baseline status for the by-group/cohort analysis.

Subjects will be prompted once or twice per week to report if the subjects have any of the following symptoms: cough, shortness of breath, difficulty breathing, fever $\geq 37.8^{\circ}\text{C}$, fatigue, myalgia, chills, wheezing, nasal congestion, runny nose, sore throat, headache, diarrhea, or new olfactory and taste disorders.

A COVID-19 symptoms log listing these symptoms will be provided to subjects with RT-PCR-confirmed COVID-19 disease (refer to Appendix 4 for an example symptom log).

If any of these symptoms are observed, the Investigator will collect appropriate samples as soon as feasible and locally perform RT-PCR and/or serological assays as locally available to evaluate for infection with SARS-CoV-2. If a serological assay is performed, this should look at antibodies against N protein antigen, but not to antibodies against Spike viral antigen, as this is part of the vaccine. These assays will be repeated 7 to 14 days after the initial assessment.

Any subject with clinical suspicion of SARS-CoV-2 infection will undergo appropriate testing and referral within the local healthcare system as appropriate. Subjects with confirmed SARS-CoV-2 infections during the trial should not receive any additional vaccine dose, but will be closely monitored for disease patterns and severity. In order to assess severity of disease, subjects will document disease progression on a symptom log and Investigators will document additional clinical parameters based on hospital records, if applicable.

The currently available case definition for COVID-19 disease is provided in Appendix 5.

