Appendix 5 Case Definition for COVID-19 Disease

According to CEPI's guidance "*COVID-19 Efficacy Endpoints in Interventional Trials: What Constitutes an Incident Clinical Disease Case and What Triggers Diagnostic Work-Up Version 2.0 dated 25 June 2020*", virologically-confirmed COVID-19 disease is defined as follows:

An RT-PCR-confirmed acute illness that is clinically consistent with COVID-19 based on the presence of at least 1 new-onset symptom: a) persistent cough, b) dyspnea or tachypnea (RR >20/min), c) Low peripheral capillary oxygen saturation ($\text{SpO}_2 <95\%$ on room air) as measured by pulse-oximetry, d) chest pain, e) Radiographic findings consistent with LRTD, f) fever (defined as body temperature of $\geq 37.8^\circ\text{C}$, irrespective of method), g) myalgia, h) chills, i) loss of smell or taste, j) headache, k) sore throat, l) diarrhea.

There will likely be further updates to this guidance, and the Sponsor will take these into consideration during the course of the trial.

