
Evaluation of infection
 
 
Number of subjects with virologically-confirmed SARS-CoV-2 infection as measured by RT-PCR.
 
	
Subjects who were unblinded and/or received an authorized/licensed COVID-19 vaccine will be censored at the day after unblinding and/or vaccination receipt. Excluding subjects who had a COVID-19 infection at baseline.
 
Safety set.
 
The number and percentage of subjects by group at baseline and by post-baseline time points with a positive RT-PCR result

ENDPOINTS (subject level)	ESTIMANDS (population level)
PCR at clinically determined time points throughout the trial. 
 
Number of subjects with asymptomatic SARS-CoV-2 infection as measured by serology at predefined time points.
 
	Immunogenicity set. The number and percentage of subjects by group at baseline and post-baseline with a positive RT-PCR result and/or infection defined by SARS-CoV-2 N-antigen and no COVID-19 symptoms.

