#### 12.9.5 Additional Exploratory Analysis

Evaluation of infection:

Number and percentages of subjects with virologically-confirmed SARS-CoV-2 infection as measured by reverse transcription polymerase chain reaction (RT-PCR) at clinically determined time points throughout the trial. This analysis will be performed on the safety set.

Number and percentages of subjects with asymptomatic SARS-CoV-2 infection as measured by serology and RT-PCR test at predefined time points.

- The definition of SARS-CoV-2 infection as measured by serology and RT-PCR results before and during the trial is outlined in sections 10.6.3.
- Subjects with a COVID-19 disease symptoms are excluded. Exclusion is based on COVID-19 cases classified as AESI. Adjudicated cases are also excluded.

This analysis will be performed on the immunogenicity set.

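### The SAP names asymptomatic infection by absence of COVID-19 symptoms but selects it by absence of a COVID-19 AESI or adjudicated case, so symptomatic infections can be counted as asymptomatic

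*SAP*

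**What the plan says.** The current protocol has no endpoint for asymptomatic infection (Protocol 4.2.3). SAP 6.1 adds one as a change from protocol, so the SAP wording alone decides what is counted.

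- **Estimand (SAP 9.4):** subjects in the immunogenicity set "with a positive RT-PCR result and/or infection defined by SARS-CoV-2 N-antigen and no COVID-19 symptoms".
- **Selection (SAP 10.6.4):** "The selection of asymptomatic subjects will be based on the exclusion of subjects with adverse events of special interest indicating COVID-19 disease".
- **Analysis (SAP 12.9.5):** it first says that subjects with symptoms of the disease drop out, then gives the means: "Exclusion is based on COVID-19 cases classified as AESI. Adjudicated cases are also excluded".
- **Who is infected (SAP 10.6.3, which SAP 12.9.5 adopts):** besides the central N-antigen ELISA, "If either the PCR swab performed post-baseline or the local ELISA serology assessment collected post-baseline is seropositive, the subject is seropositive at that visit" and from then on.
- **Work-up of symptoms (Protocol 9.3):** subjects are prompted once or twice a week. If a listed symptom occurs, the site is to "locally perform RT-PCR and/or serological assays as locally available to evaluate for infection with SARS-CoV-2". Table 1 schedules a swab on Day 1 only; its footnote q adds swabs for symptoms, where operationally possible.
- **Case definition (Protocol Appendix 5):** "An RT-PCR-confirmed acute illness that is clinically consistent with COVID-19 based on the presence of at least 1 new-onset symptom", followed by the list of qualifying symptoms.

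**The concern.** The estimand turns on whether the subject had symptoms. The two operational sections turn on whether someone reported or adjudicated a COVID-19 case. Neither uses the replies to the symptom prompts, the fact that a test was done because of symptoms, or the diary and AE records.

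The only case definition in the documents requires RT-PCR, while infection status does not. That leaves room for subjects who are infected under SAP 10.6.3, had symptoms, and never became a reported case. If they are left in, the count mixes silent infection with mild or non-PCR-confirmed illness. The mix would then depend on which tests a site had and how it reported AESIs, neither of which is a property of the vaccine.

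**Working it through.** No figure in the plan relates to this endpoint, so there is none to reproduce. The check compares the symptom lists and then traces subject profiles through the rules.

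**Symptom lists.** Protocol 9.3 prompts for 14 symptoms: cough, shortness of breath, difficulty breathing, fever, fatigue, myalgia, chills, wheezing, nasal congestion, runny nose, sore throat, headache, diarrhea, and new smell or taste disorder. Ten have a counterpart in Appendix 5, although cough qualifies there only if persistent. The other 14 − 10 = 4 (fatigue, wheezing, nasal congestion, runny nose) have none.

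**Trace.** Infected is judged by SAP 10.6.3, counted by SAP 10.6.4 and 12.9.5, and the last column by the SAP 9.4 wording.

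| Profile | Infected? | Counted as asymptomatic? | Asymptomatic under 9.4? |
|---|---|---|---|
| A. Symptoms; RT-PCR negative or not done; local N-serology positive; no COVID-19 AESI, not adjudicated | Yes | Yes | No |
| B. RT-PCR positive; only one or more of the 4 unlisted symptoms; no COVID-19 AESI, not adjudicated | Yes | Yes | No |
| C. Symptoms; no local test done; later scheduled N-antigen sample positive; no COVID-19 AESI, not adjudicated | Yes | Yes | No |
| D. A, B or C, but reported as a COVID-19 AESI or adjudicated | Yes | No | No |
| E. Symptoms; all tests negative | No | No | No |
| F. No symptoms; scheduled N-antigen sample positive | Yes | Yes | Yes |

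The rules agree with the estimand for D, E and F and depart from it for A, B and C. Each departure needs three things together: symptoms, evidence of infection, and no COVID-19 AESI or adjudication.

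**RT-PCR as a source.** The only scheduled swab is on Day 1. A later positive from protocol-directed testing therefore comes from a swab taken because of symptoms. If any of those symptoms is in Appendix 5, the subject meets the case definition and should be reported and removed. What remains is profile B, so this is not a further route. It does show that a post-baseline RT-PCR positive is a poor marker of asymptomatic infection unless the reason for the swab is considered.

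**The case against.** The strongest reply is that AESI reporting is not limited to RT-PCR-confirmed disease. Protocol 9.1.1.3 and SAP 10.5.5 list COVID-19 disease as an AESI with no RT-PCR condition. Protocol 3.3.1 asks for a work-up of any suspected AESI. SAP 10.6.4 speaks of events that indicate the disease, which is broader than confirmed cases, and loss of smell or taste is an AESI in its own right. Appendix 5 defines virologically confirmed disease, a narrower term. The example symptom log in Appendix 4 includes fatigue, runny nose and wheezes, so sites might well treat profile B as COVID-19 disease. On adjudication, confirmation is a question put to the committee (SAP 10.9), and SAP 12.9.5 removes adjudicated cases without requiring a positive answer. SAP 12.9.5 also states the right intention.

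All of this stands, and it rules out the reading that every symptomatic subject who fails the RT-PCR case definition is counted as asymptomatic. Such a subject is counted only with evidence of infection and only if no AESI was reported and no adjudication took place. The gap is still open, because the documents nowhere require a COVID-19 AESI for a symptomatic subject with positive serology alone. Protocol 9.3 also gives the symptom log only to RT-PCR-confirmed subjects.

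A reader might also infer that the error would carry into pooled analyses. The Synopsis rationale and Protocol 10.3.1 speak of pooling COVID-19 disease cases, not asymptomatic infections, so the documents do not support that. In addition, all RT-PCR positives are tabulated separately, whatever the symptoms, under the virologically confirmed endpoint.

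**Conclusion.** The mismatch is real: SAP 10.6.4 and 12.9.5 implement a looser condition than SAP 9.4 states, and following them literally can place symptomatic infections in the asymptomatic count. The direction is towards overstating that count.

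The size cannot be derived. The documents give no infection rate, no share of symptomatic infections diagnosed by serology alone and no AESI reporting rate, so any percentage would be an assumption. If sites report every symptomatic infection as a COVID-19 AESI, the effect is zero; it grows as reporting follows Appendix 5 more strictly.

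The endpoint is exploratory and descriptive, with no inference or sample size attached, and no primary or secondary result changes. The correction is worth making because the count would otherwise not measure what it is named for.

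**What to change.** Put one definition in SAP 9.4, 10.6.4 and 12.9.5. Count an infection as asymptomatic only if all of these hold:

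1. no positive RT-PCR or local serology from a test triggered by symptoms;
2. no COVID-19 AESI;
3. no adjudicated case;
4. no recorded COVID-19 symptom (prompt replies, AE and diary records) in a stated window before the first positive sample.

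Condition 4 is needed for profile C, where no symptom-triggered test exists. Keep RT-PCR positives from swabs not triggered by symptoms, such as the scheduled Day 1 swab. State in SAP 10.5.5 or 10.6.4 whether a COVID-19 AESI requires RT-PCR confirmation.

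Tabulate infections with symptoms, or with a positive symptom-triggered test, that were not reported as COVID-19 cases in a separate row labelled symptomatic infection not meeting the case definition. Query any that prove to meet Appendix 5.

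The cost is SAP wording, one table row and some programming; the test results are already needed for SAP 10.6.3. There are two limits. The documents do not say how prompt replies are stored, and diaries collect unsolicited AEs only for each vaccination day and the following 28 days, so later symptoms rest mainly on the prompts. The asymptomatic count will also be slightly smaller, and some vaccine reactions will be classed as symptoms: 6 of the 14 prompted symptoms (fever, fatigue, myalgia, chills, headache, diarrhea) are also solicited systemic events. Those subjects stay visible in the separate row.

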### 10.6.5 Cell-Mediated Immunity

CMI will only be evaluated in approximately 20 subjects per CVnCoV group at assigned site(s). The frequency and functionality of SARS-CoV-2 spike-specific T-cell response after antigen stimulation will be determined in PBMC in comparison to baseline Innate Immune Response

The innate immune response will only be evaluated in approximately 20 subjects per CVnCoV group at assigned site(s) by measuring serum cytokines, including but not limited to IFN- $\alpha$ , IFN- $\gamma$ , IL-6, CCL 2, and IP 10.

## 10.7 Geometric Mean

The RBD IgG ELISA and virus neutralizing antibodies are expressed as GMT (geometric mean of reciprocal duplicate dilutions). It is assumed that the data is skewed hence the geometric mean (GM) and geometric standard deviation (GSD) will be presented. The GM is calculated as the anti-logarithm of the mean of the log-transformed data. The GSD will be calculated as the anti-logarithm transformation of the standard deviation of the log-transformed data.

## 10.8 Censoring Rules for Subjects Unblinded and/or Treated with Alternate Licensed/Authorized Vaccine

Since the efficacy results from Trial CV-NCOV-004 are available and all subjects in this trial are currently eligible to receive a licensed/authorized vaccine, all subjects in this trial will be unblinded following protocol version 3.0. Hence, all subjects will be unblinded prior end of the trial, and their data will be censored in all analyses. The below rules are still applicable as subjects could request unblinding or became eligible to receive a licensed/authorized vaccine prior to the protocol V3.0.

The following censoring rules will be applied to these subjects to avoid any study bias.

- Subjects who are unblinded will be censored for the safety endpoints at the first day after unblinding. Any related follow-up data that is collected from censoring time point forward will be included in the listings output.
- Subjects who are unblinded but decide not to receive the alternate licensed/authorized vaccine and to stay in the study will be analyzed for immunogenicity as planned.
- Subjects who are unblinded, but decide to receive the alternate licensed/authorized vaccine, will have their immunogenicity data censored at the first day after receiving the alternate licensed/authorized vaccine. However, any related follow-up data that is collected from this time point forward will be included in the listings output.
- Subjects who received an alternate licensed/authorized vaccine without or before being unblinded will be censored for safety and immunogenicity at the first day after receiving the alternate licensed/authorized vaccine. As described above, data collected from the censoring timepoint forward will be included in the listings output.

This is summarized in Table 7.

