9.2 Immunogenicity Assessments

An overview of the timing of blood sample collection for immunogenicity assessment is provided in Table 1.

Unused samples may be used for assay validation and additional studies of the mechanism of action of the vaccine.

If a subject receives a licensed/authorized vaccine, no further immunogenicity samples will be collected/analyzed after receipt of the licensed/authorized vaccine. Immunogenicity samples on Day 393 will only be collected from subjects who attend this visit at the site,

ie, subjects who received the Day 180 booster AND who had not received a licensed/authorized vaccine before this visit.

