### 9.4 Estimands

ENDPOINTS (subject level)	ESTIMANDS (population level)
Primary Safety	

The frequencies, intensities, and duration of solicited local AEs on Day 1 and Day 29 and the following 7 days by dose and group.
 
The frequencies, intensities, duration, and relationship to trial vaccination of solicited systemic AEs on Day 1 and Day 29 and the following 7 days by dose and group.
 
The occurrence, intensity and relationship to trial vaccination of unsolicited AEs on each vaccination day and the following 28 days by dose and group.
 
The occurrence and relationship to trial vaccination of SAEs and AESIs throughout the trial.
	
Safety set. Subjects who were unblinded and/or received an authorized/licensed COVID-19 vaccine will be censored at the day after unblinding and/or vaccination receipt.
 
The number and percentage of subjects overall and by dose level:
 
Each solicited local AE within 7 days after each trial vaccination by intensity and overall.
 
Each solicited systemic AE within 7 days after each trial vaccination by intensity, by relationship to trial vaccine and overall.
 
The mean duration in days by group with standard deviation of solicited AEs (within the solicited period, total duration).
 
At least 1 unsolicited AEs, at least 1 grade unsolicited AEs and each unsolicited AEs by SOC/PT occurring within 28 days after each trial vaccination and overall by causal relationship to trial vaccine and overall.
 
At least 1 SAE, or at least 1 AESI to vaccine overall by causal relationship to trial vaccine and overall.

ENDPOINTS (subject level)	ESTIMANDS (population level)
Primary Immunogenicity	

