
Day 57 (only for subjects receiving the booster dose on Day 57),
 
Day 85 (only for subjects receiving the booster dose on Day 57),
 
Day 180 (only for subjects receiving the booster dose on Day 57 or Day 180),
 
Day 208 (only for subjects receiving the booster dose on Day 180), and
 
Day 393 (only for subjects receiving the booster dose on Day 180):
 
 
The proportion of subjects seroconverting for SARS-CoV-2 spike protein antibodies, as measured by ELISA.
 
Individual SARS-CoV-2 spike protein-specific antibody levels in serum, as measured by ELISA.
 
GMTs of serum SARS-CoV-2 spike protein antibodies, as measured by ELISA.
 
	
Immunogenicity set. Applicable for subjects who received a booster dose at day 57 or day 180. Subjects receiving an authorized/licensed COVID-19 vaccine during the course of the trial will be censored at the day after intake.
 
Sensitivity analysis: In addition, the secondary immunogenicity endpoint will be repeated for subjects who received dose 1 and dose 2 (and if eligible and received a booster dose at day 57 or day 180) of trial vaccine and for whom the baseline blood sample for immunogenicity assessment and day 43 are available for analysis and no major protocol deviations expected to impact the immunogenicity outcomes. Subjects receiving an authorized/ licensed vaccine during the course of the trial will be censored at the day after receiving the authorized/ licensed vaccine. Subjects exposed to SARS-CoV-2 prior to the trial will be excluded. Subjects will be excluded at the time point they have been exposed to SARS-CoV-2.
 
Estimate of subjects seroconverted (SARS-CoV-2 spike protein-specific antibodies) with 95% credibility interval using prior beta(1.9, 0.1)
 
Number and percentage with exact 95% confidence intervals of subjects for who a seroconversion is

ENDPOINTS (subject level)	ESTIMANDS (population level)

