**Table 7 Censoring Rules for Subjects Unblinded Prior to Protocol Version 3.0**

Analysis	Treatment Received in CV-NCOV-002	Alternate Licensed/Authorized Vaccine Received?	Censoring Rule
Safety	CVnCoV	No Yes	Censored at the first day after unblinding
	Active Control	No Yes	
Immunogenicity	CVnCoV	No	Analyzed as planned
		Yes	Censored at the first day after receiving the alternate licensed/authorized vaccine.
	Active Control	No	Analyzed as planned
		Yes	Censored at the first day after receiving the alternate licensed/authorized vaccine

The following details are to be followed regarding censoring the day after unblinding:

- Unblinding day ( = Pacific Time Zone) must be adjusted to the subject's time zone.
- Unblinding time does not matter for anything apart from the above time zone normalization. (As case start time is not collected.)
- If the case start day and the unblinding day occur on the same day the case will count for the analysis. (Censoring starts at the day after the unblinding.)

The following details are to be followed regarding censoring the day after receiving the alternate licensed/authorized vaccine:

- Times are not relevant as neither alternate licensed/authorized vaccine time nor case start time are collected.
- If alternate licensed/authorized vaccine date is complete then censoring starts at first day after the alternate licensed/authorized vaccine day.
- If alternate licensed/authorized vaccine date is incomplete (only day missing) then censoring starts after this month.
- If alternate licensed/authorized vaccine date is incomplete (month missing, year available) then censoring starts after this year.
- If alternate licensed/authorized vaccine date is completely missing then no censoring can be made.

As these imputations of incomplete licensed vaccine dates are not an ideal solution this is only to be considered as a fallback solution in case complete licensed vaccine dates cannot be retrieved and an interim workaround for unclean data during study conduct.

All incomplete or missing licensed vaccine dates need to be queried.

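### SAP 10.8 censors all data of subjects unblinded under protocol v3.0, in conflict with SAP 9.4, and on one reading this removes Day 393 booster antibody samples

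*SAP*

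**What the plan says.** **SAP 10.8.** After noting that protocol version 3.0 unblinds everyone, the section states: "Hence, all subjects will be unblinded prior end of the trial, and their data will be censored in all analyses". It continues: "The below rules are still applicable as subjects could request unblinding or became eligible to receive a licensed/authorized vaccine prior to the protocol V3.0". The bullets that follow separate safety from immunogenicity. For subjects who are unblinded, decline another vaccine and decide "to stay in the study will be analyzed for immunogenicity as planned". Table 7 summarises the bullets under the title "Censoring Rules for Subjects Unblinded Prior to Protocol Version 3.0".

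**SAP 9.4.** For primary and secondary immunogenicity the only censoring trigger is another vaccine: "Subjects receiving an authorized/licensed COVID-19 vaccine during the course of the trial will be censored at the day after intake". For primary safety, unblinding is a trigger too: "Subjects who were unblinded and/or received an authorized/licensed COVID-19 vaccine will be censored at the day after unblinding and/or vaccination receipt". Secondary safety and the infection endpoints follow the safety pattern.

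**Day 393.** Protocol 9.2, repeated in SAP 10.6, limits Day 393 antibody sampling to "subjects who received the Day 180 booster AND who had not received a licensed/authorized vaccine before this visit". SAP 9.4 names Day 393 as a secondary immunogenicity time point, and SAP 12.9.2 includes it in the booster analysis.

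**The concern.** SAP 9.4 deliberately uses two triggers: unblinding for safety and infection, and another vaccine for antibodies. The 10.8 sentence removes that distinction for everyone unblinded under version 3.0. The text that would restore it is tied, by its lead-in and by the title of Table 7, to subjects unblinded earlier.

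A programmer who follows 10.8 as written could treat two boosted subjects differently when neither has had another vaccine. One unblinded on request would keep the Day 393 result, and one unblinded by the amendment would lose it. The SAP gives no reason for such a split.

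Day 393 is the antibody time point most exposed. SAP 11.1 reports that the interim analysis of the booster to Day 208 has already been performed, so the primary time points and the earlier booster time points probably precede version 3.0. Removing Day 393 would withdraw a secondary time point after blood had been drawn for it. SAP 6.1, which lists changes from the protocol, declares no such change.

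**Working it through.** The plan states no figure on this point, so the check is a comparison of text, followed by a count, a date calculation and an illustration of precision.

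**1. The rules side by side**

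| Endpoint | SAP 9.4 trigger | 10.8 bullets and Table 7 (tied to before v3.0) | 10.8 sentence on v3.0 unblinding |
|---|---|---|---|
| Safety | Unblinding or licensed vaccine | Unblinding; licensed vaccine if that comes first | Censored, no date |
| Infection, including asymptomatic | Unblinding or licensed vaccine | Not mentioned | Censored, no date |
| Spike and neutralizing antibodies | Licensed vaccine only | Licensed vaccine only | Censored, no date |

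The columns disagree on the trigger only in the antibody row. The missing date affects all three rows.

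**2. What the sentence can mean**

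- (a) All data of all subjects are removed. This would empty every analysis, including Days 29 and 43, and cannot be intended.
- (b) All endpoints are censored from the day after unblinding. Day 393 antibody samples drawn after that day are lost.
- (c) Only safety and infection endpoints are meant. Nothing is lost, but the words covering all analyses and the title of Table 7 are then wrong.

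**3. Subjects at stake.** SAP Table 1 plans Day 180 boosters for 30 subjects in Group 3 and 30 in Group 4: 30 + 30 = 60. Visit 9 excludes anyone already given a licensed vaccine, so under 9.4 every sample collected there is free of vaccine censoring. Under (b), those drawn after unblinding are not used.

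**4. Timing.** Assume that 12 µg enrolment began no earlier than protocol version 2.0 (20 October 2020). Nominal Day 393 is 392 days after Day 1.

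- Earliest nominal Day 393: 20 October 2020 + 392 days = 16 November 2021.
- Day 1 that puts nominal Day 393 on the date of version 3.0: 3 December 2021 − 392 days = 6 November 2020.

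On that assumption, any subject with Day 1 after 6 November 2020 has a nominal Day 393 after the date of version 3.0. Visit windows shift individual dates, and each subject's unblinding date is unknown, so the split between samples before and after unblinding cannot be computed.

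**5. Precision.** SAP 10.5.10 with the Beta(1.9, 0.1) prior gives the estimate (x + 1.9)/(n + 2), with limits from Beta(x + 1.9, n − x + 0.1). It reproduces SAP Table 3: 86 of 90 gives 87.9/92 = 95.5% (90.5 to 98.7). With assumed counts:

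- 57 of 60: 58.9/62 = 95.0% (88.4 to 98.9)
- 14 of 15: 15.9/17 = 93.5% (78.3 to 99.8)
- no subjects: 1.9/2 = 95.0% (52.1 to 100)

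The last line is the prior alone. If no sample survived censoring, the formula would still return 95%.

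**The case against.** The strongest reply is that this is loose wording which the rest of the SAP resolves. SAP 9.4 separates the triggers clearly. SAP 10.6 provides for Day 393 sampling, and 12.9.2 plans its analysis. The bullets in 10.8 speak of unblinded subjects without a date limit and are said still to apply. On that view the sentence was meant for safety. This is plausible and may be the intent. It still leaves a sentence that says the opposite and a table title that excludes the subjects concerned, in a section that the SAP change history shows was revised for this very unblinding.

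A reader might infer that the SAP plans to drop the Day 393 endpoint, or that the route of unblinding settles the matter. The documents do not support either as fact. The sentence gives no start date, so the Day 393 loss comes from reading (b) and not from the bare words. The narrow scope of the bullets is supported by their lead-in and by the title of Table 7, but it is not compelled.

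Three further replies stand in part.

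- The booster is open-label and planned only in CVnCoV groups, so recipients could be regarded as unblinded before version 3.0. The SAP does not say whether a booster counts as unblinding.
- Data after censoring remain in listings, and the trial is descriptive, so one late secondary time point is at stake and no confirmatory result.
- Knowing the assignment does not alter an assay reading, but it could alter exposure to infection, and the main secondary analysis does not exclude infected subjects. This is a reason to settle the rule explicitly. SAP 9.4 already chose not to censor antibodies at unblinding.

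**Conclusion.** The conflict between SAP 10.8 and SAP 9.4 is real and should be corrected before database lock. For subjects unblinded under version 3.0, 10.8 states censoring without a date or an endpoint, while 9.4 limits antibody censoring to receipt of a licensed vaccine.

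The consequence is conditional. On reading (b), Day 393 antibody results drawn after unblinding leave the secondary booster analysis. At most 60 planned subjects are affected, fewer after licensed vaccination or dropout. The share of collected samples lost could range from none to nearly all. The high end rests on the assumed start of 12 µg enrolment and on unblinding having preceded the Day 393 visit; the documents establish neither. The precision figures rest on assumed counts and only illustrate the effect.

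**What to change.** Replace the 10.8 sentence. Deleting only its reference to all analyses would not be enough, because it would still say that the data are censored, without a date or an endpoint. The replacement should state, for subjects unblinded by any route (on request or under version 3.0):

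- Safety and infection endpoints are censored from the day after unblinding or licensed vaccination, whichever is earlier. Asymptomatic infection belongs here. It is analysed on the immunogenicity set but censored at unblinding in 9.4, so a blanket exemption for immunogenicity data would contradict 9.4.
- Spike and neutralizing antibody endpoints are censored only from the day after a licensed/authorized SARS-CoV-2 vaccine, as in 9.4.

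Align the lead-in to the bullets, and retitle Table 7 so that it covers all unblinded subjects. The cost is a short text edit in the SAP and a check that the analysis programs follow it. No new data are needed.
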